3.4.3.3 Safety

The likelihood of safety issues is minimal with bedwetting alarms. Any major safety events will be reported. Also patients who drop out due to excess startling or unwillingness to continue to wear the alarm will be considered failures and included as such in the data analysis.

3.4.3.4 Analysis of Subject Characteristics

Age and sex of patients in each group
 Dvq scores of each group

3.4.3.5 Interim Analysis (if applicable)

interim analysis will be done a midpoint to evaluate ages of groups so we can make adjustments to have an age matched cohort.

3.4.3.6 Health economic evaluation

The cost of therapy with SNEA vs GoGoband® over a 3 month period will be evaluated

3.4.3.7 Other

3.4.4 Subsets and Covariates

3.4.5 Handling of Missing Data

Patients who drop out of the study will be considered failures for purposes of the study with regards to success vs partial or failure analysis
 Dry /wet night rates will be maintained for the overall analysis of overall dry/wet ratios regardless of the patient ceases participation

4 Trial Administration

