Randomized Study Of Novel Enuresis Alarm (GoGoband®)Vs Standard Bedwetting Alarm

Protocol Number
2000031281

NCT05214131

Protocol Version
February 20, 2024
Version #6

IDE Number:

IDE Holder:

PRINCIPAL INVESTIGATOR:

[name]., Ph.D.
Department of Urology
[contact]
Email Address: [contact]

Confidentiality Statement:

2000031281

February 20, 2024

REVISION HISTORY:

Include the IRB approved protocol version number and date for each revision of the protocol. All version history should remain in the table and never be deleted. The oldest IRB approved version of the protocol should be listed on the top row. The most recent IRB approved version should be listed on the bottom row.

Revision #	Version Date
1	Sept 1 2021
2	Sept 9 2021
3	November 18, 2021
4	December 28, 2021
5	Jan 15 2022
6	February 20, 2024

2000031281

February 20, 2024

Synopsis

Primary Objective
 
Identify the dry night rate in patients using the GoGoband® nocturnal enuresis device vs a standard Pflaunger bedwetting alarm.

Secondary Objective (if applicable)
 
to ascertain if familial incidence of nocturnal enuresis has an effect on outcomes

Study Duration: total 3 years, 2 years active with 1 year for analysis

Study Design
 
Include a high-level description of the study design.
 
This is a prospective randomized comparison of GoGoband® vs standard nocturnal enuresis alarm

Number of Study Sites
 
Study sites will include all clinic sites where patients are seen in the Yale New Haven Health System
 
Yale New Haven Children’s Hospital clinic WP2 Yale New Haven Children’s Hospital Longwharf Clinic Yale New Haven Children’s Hospital Trumbull clinic Yale New Haven Children’s Hospital Norwalk clinic Yale New Haven Children’s Hospital Greenwich Clinic

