2.2 Background/prevalence of research topic

Urologic literature recognizes that enuresis alarm treatment for nocturnal enuresis is a form of behavioral therapy. It works in conjunction with both positive reinforcement and aversive negative experiences and has been shown to be effective after Mowrer and Mowrer introduced it in 1938. Unfortunately, the literature, using the current effectivity standard of maintaining four weeks of dry nights criteria from the International Children's Continence Society consensus document, reveals that it is not as effective as it is stated. Using the new standard, there are few publications that have success rates that exceed 50%^{2,3}. When the published abandonment rates (~30%) and relapse rates (~50%) are taken into consideration, the effectivity of current enuresis alarm treatment is further reduced to only 25-33%. Innovation in enuresis alarm treatment for pediatric enuresis has been stagnate for the last 30 years and clearly a better method of enuresis alarm treatment in children is necessary.

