3.3.6 End of Study and Follow-up

Patients who withdraw from the study due to lack of efficacy of the treatment will then be allowed to continue regular treatment options afforded to patients with MNE.

Patients that failed alarm therapy will be candidates to start treatment with desmopressin and if they fail that they can proceed to the addition of additional medications such as imipramine, atomoxetine, guanfacine or oxybutynin

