3.3.7 Removal of subjects

Non-compliant patients will be removed from the study. Alarms will not be requested back from the participants.

Reasons for noncompliance will be the following

1. Not using device
2. Not filling in and submitting monthly logs.

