3.4.3 Planned Analysis

3.4.3.1 Primary Analyses

Outcomes will be evaluated between the 2 groups using crosstab analysis of the data for the following data :

Wetting event: Dry or Wet

Did patient wear the device: yes or no used to measure compliance

Did patient take the medication: yes or no used to measure compliance
 Is the patient considered cured (dry 29/30 nights) : yes or no
 Is the patient partially better (improvement of 50% or more compared to pretreatment)
 Does the patient show no improvement (<50% improvement compared to Pretreatment)
 Logistic regression analysis may be performed on the incremental wet dry data vs time to achieving dryness

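### The dry-night ratio keeps only a drop-out's pre-exit nights, so if losses of poor responders differ between arms, the pooled rate favours the arm that loses more of them

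*Combined protocol and SAP*

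**What the plan says.** Section 3.4.5 (Handling of Missing Data) has two rules for the same child. For the categorical outcome: "Patients who drop out of the study will be considered failures for purposes of the study with regards to success vs partial or failure analysis". For the nightly outcome: "Dry /wet night rates will be maintained for the overall analysis of overall dry/wet ratios regardless of the patient ceases participation". It gives no rule for nights after exit, no weighting by child and no sensitivity analysis.

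The nightly outcome matters. The synopsis states the primary objective as "Identify the dry night rate in patients using the GoGoband® nocturnal enuresis device" against a standard alarm. Wet or dry is the first primary outcome variable in section 5.2.1 and the first item under section 3.4.3.1, where "Outcomes will be evaluated between the 2 groups using crosstab analysis of the data for the following data" introduces the list.

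The plan expects children to leave. Section 3.3.6 refers to "Patients who withdraw from the study due to lack of efficacy of the treatment", and section 3.3.7 says "Non-compliant patients will be removed from the study". Section 3.2.1 (Potential Risks) adds startle and, for GoGoband only, inadequate home internet. Section 3.4.3.3 makes startle and unwillingness drop-outs failures but does not say what happens to their nights. The study schedule has no nightly data collection after exit.

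**The concern.** In a crosstab of nights, each child's weight is the number of nights contributed. A child who leaves at day 30 supplies 30 nights and a completer supplies 90. If those who leave early are mostly the wetter children, their wet nights drop out of the denominator and the arm's rate rises. If the two arms lose such children unequally, part of the observed difference comes from attrition and not from the devices.

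The cure outcome gives no such gain, because there the same children are failures. The two headline results could therefore disagree for identical devices, and the plan gives no means of seeing why.

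**Working it through.** **Figures in the plan.** No figure in the plan covers the dry-night rate under attrition. The sample size in section 3.4.2 reproduces and is not in dispute: (0.5×0.5 + 0.8×0.2) × ((1.645 + 0.842)/0.3)² ≈ 28.2, rounded up to 29 per arm. That section states no drop-out allowance.

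**Are nights pooled?** The wording of 3.4.5 and the crosstab in 3.4.3.1 point that way, and so does the team's practice. The 60-patient crosstab in section 2.1.2 counts nights: (2776 + 694) + (560 + 169) + (661 + 82) = 3470 + 729 + 743 = 4942 nights from 60 children.

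**Inputs.**
- From the plan: 90 nights per child (section 5.1.1). The 30% loss is borrowed from section 2.2: "When the published abandonment rates (~30%) and relapse rates (~50%) are taken into consideration".
- Assumed: 70% of children dry on 70% of nights, 30% dry on 20%, rates constant over time, only poor responders leave, and exit is at day 14, 30 or 45.

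The rate with full follow-up is 0.7×0.7 + 0.3×0.2 = 55% in both arms.

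**Formula.** With a share L of all children leaving at day d:

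pooled rate = [0.7×90×0.7 + (0.3−L)×90×0.2 + L×d×0.2] / [0.7×90 + (0.3−L)×90 + L×d]

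At day 30:
- L = 0.30: (44.1 + 0 + 1.8)/(63 + 0 + 9) = 45.9/72 = 63.8%
- L = 0.15: (44.1 + 2.7 + 0.9)/(63 + 13.5 + 4.5) = 47.7/81 = 58.9%
- L = 0: 49.5/90 = 55.0%

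| Exit day | 30% leave | 15% leave | None leave | Gap, 30% vs 15% | Gap, 30% vs none |
|---|---|---|---|---|---|
| 14 | 66.9% | 60.1% | 55.0% | 6.8 | 11.9 |
| 30 | 63.8% | 58.9% | 55.0% | 4.9 | 8.8 |
| 45 | 61.2% | 57.8% | 55.0% | 3.3 | 6.2 |

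Equal losses on the same day give a gap of 0.

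**Second set of assumptions.** Take 50 children per arm, 25 dry on 90% of nights and 25 on 30% (true rate 60%), with 15 against 5 poor responders leaving at night 30.
- 15 lost: (25×90×0.9 + 10×90×0.3 + 15×30×0.3)/(25×90 + 10×90 + 15×30) = 2430/3600 = 67.5%
- 5 lost: (25×90×0.9 + 20×90×0.3 + 5×30×0.3)/(25×90 + 20×90 + 5×30) = 2610/4200 = 62.1%
- False gap: 5.4 points

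**Rates that rise over time.** Let the 25 responders rise linearly from 30% to 100% and the 25 others from 20% to 40%, with exit at night 30. Full follow-up gives 47.5%. Losing 5 or 15 poor responders gives 48.5% or 51.0%. Losing 15 children who would later have responded gives 40.2%, so the shift reverses.

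**Alternatives, for identical devices.**
- One equally weighted rate per child: 55% in the first example and 60% in the second, whatever the losses. With rising rates a small residue remains, against the arm that loses more: 45.5% (15 poor responders lost) and 46.8% (5 lost), against 47.5%.
- Post-exit nights scored wet over 90 nights: 45.9/90 = 51.0% against 47.7/90 = 53.0% in the first example (exit at day 30), and 2430/4500 = 54.0% against 2610/4500 = 58.0% in the second. The false difference now goes the other way.

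**The case against.** - **The sentence in 3.4.5 is unclear.** It could mean that each child's rate is carried as it stood at exit, which gives 55% in the first example. That reading is possible. But the wording about overall ratios, the crosstab and the pooled pilot table make retention of recorded nights the likelier one, and the ambiguity itself needs resolving.
- **A reader might infer that any abandonment raises the rate.** The documents do not support that. Non-compliance, missing logs and internet failure need not track response, and section 5.3.2 already requires home WiFi. GoGoband begins with a training phase: in the pilot's highest compliance group, dry nights went from 48.1% in training to 96.0% in weaning. Early exit by later responders is therefore plausible, and it lowers the pooled rate.
- **A reader might take 6 to 12 points as the expected bias.** That range needs every poor responder to leave one arm and nobody to leave the other. The 30% in section 2.2 is a published overall figure for alarms, not a difference between arms.
- **A reader might infer that no clustering method would help.** Robust standard errors on pooled nights would leave the estimate shifted. One equally weighted rate per child removes the shift when each child's rate is constant.
- **The two rules answer different questions, and cure gives some protection.** Both are true. Cure with drop-outs as failures is a useful check, but it does not correct the dry-night rate, which the synopsis names as the primary objective.

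**Conclusion.** The point holds in conditional form. As most naturally read, the plan weights the dry-night rate toward children who stay. It has no safeguard if exit is related to response and losses differ between arms. On the stated assumptions with exit at day 30, the false difference is about 5 points with 30% against 15% leaving, about 9 with 30% against none (12 at day 14), and 0 with equal losses. The sign depends on who leaves: early exit by later responders reverses it.

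Responder share, dry rates, exit days and the split of losses are assumptions. The documents do not show which arm will lose more children, so they do not support a claim that the rule favours GoGoband or the standard alarm. The rule should be changed because the repair uses data already collected and affects what can be concluded on the primary objective.

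**What to change.** In section 3.4.5, and to match in 3.4.3.1:

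1. Make the main dry-night analysis one proportion per randomised child, with children weighted equally, instead of pooled nights. State what is done with a child who has no recorded nights.
2. Add a sensitivity analysis with a 90-night denominator for every randomised child, scoring nights after exit as wet. This follows the section's own failure rule. Apply it to all exit reasons: lack of efficacy, startle or unwillingness, non-compliance or missing logs, and internet failure.
3. Report the pooled observed-night ratio beside these, with nights contributed and exits by reason in each arm.

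Fix the rule before results by arm are examined. The cost is a few sentences, one table and a little more analysis. The wet-scored version is conservative and penalises the arm with more exits, so it belongs as a sensitivity analysis and not as the only result.

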4.1 Ethical Considerations: Informed Consent/Assent and HIPAA Authorization

4.2 Institutional Review Board (IRB) Review

The protocol will be submitted to the IRB for review and approval. Approval of the protocol must be obtained before initiating any research activity. Any change to the protocol or study team will require an approved IRB amendment before implementation. The IRB will determine whether informed consent and HIPAA authorization are required.

The IRB will conduct continuing review at intervals appropriate to the degree of risk, but not less than once per year.

A study closure report will be submitted to the IRB after all research activities have been completed.

Other study events (e.g. data breaches, protocol deviations) will be submitted per [Yale University IRB's policies.

4.3 Subject Confidentiality

Subject confidentiality is held in strict trust by the research team. Subject medical record review will be limited to the just the elements needed to complete the study. Only authorized HIPAA and GCP trained study team members will be allowed to extract research data from medical records and enter it into **Randomized Study Of Novel Enuresis Alarm Vs Standard Bedwetting Alarm** which will be maintained in a yale secure hipaa compliant box drive. No direct subject identifiers will be entered into **Randomized Study Of Novel Enuresis Alarm Vs Standard Bedwetting Alarm**. Each subject will be assigned a unique study number. A master list linking the unique study number to the human subject will be maintained in a locked drawer in FMP 308 the principal investigators office in a locked cabinet within a locked office .

4.4 Deviations/Unanticipated Problems

If the study team becomes aware of an anticipated problem (e.g. data breach, protocol deviation), the event will be reported to the IRB by e mail.

4.5 Data Collection

Data will be collected at each visit, entered by the principal investigator and then sent back to be scanned and entered into the patient's epic chart.

4.6 Data Quality Assurance

Data quality consists of data logs which need to be maintained by the patients. Other than reminding patients that the data needs to be entered we are constrained by lack of being able to record events if the patient does not. The GoGoband® system has a built in system of recording wet dry events therefore this data will be available consistently as long as the patients use the device.

4.7 Study Records

Study records will consist of the medical record which is maintained in epic DVQ which is entered into epic routinely

Logs which will be transferred to database and then retained in epic

4.8 Access to Source

Source documents such as the log forms will be entered by the principal investigator [name], PhD into a dedicated spreadsheet which will be deidentified and maintained on a Yale University protected box drive. Once data is entered the documents will be scanned and entered to Epic as media files as per routine protocol for the department of urology.

4.9 Data or Specimen Storage/Security

As mentioned before the logs and DVQ along with the medical record will be in Epic.

4.10 Retention of Records

Records will be maintained as per law for pediatric patients and as per the guidelines set forth by Yale/New Haven Health and the state of Connecticut

4.11 Study Monitoring

Study monitoring will be conducted internally

4.12 Data Safety Monitoring Plan

The risk assessment is minimal

4.13 Study Modification

No modifications are expected

4.14 Study Discontinuation

Discontinuation of the study is only expected if grant money is not forthcoming

4.15 Study Completion

We expect the study to last 2 years and will allow for 1 year for data analysis and submission of data for publication. Once completed we will notify the IRB by e-mail.

4.16 Conflict of Interest Policy

The independence of this study from any actual or perceived influence, such as by the pharmaceutical industry, is critical. Therefore, any actual conflict of interest of persons who have a role in the design, conduct, analysis, publication, or any aspect of this trial will be disclosed and managed. Furthermore, persons who have a perceived conflict of interest will be required to have such conflicts managed in a way that is appropriate to their participation in the trial. The study leadership in conjunction with the appropriate conflict of interest review committee has established policies and procedures for all study group members to disclose all conflicts of interest and will establish a mechanism for the management of all reported dualities of interest.

All investigators will follow the applicable conflict of interest policies.

4.17 Funding Source

Alarms will be provided to the patients by GoGoband® Inc. via a grant awarded to them from SouthWest Pediatric Device Consortium and American Academy Pediatrics Section of Urology Pediatric Urology Device Prize

4.18 Publication Plan

Once the study is completed the study will be presented at the American Urological Association and later published in the Journal of Urology

2000031281

February 20, 2024

5 Appendices

Appendix #	Title	Section	Topic
1	flowchart		
2	alarm log		
3	email to pediatricians for recruitment		
4	Prescreening questions for Care center for patients calling in regarding the study		
5			

2000031281

February 20, 2024

6 List of Tables

Table of actions and timelines
